7.6 Criteria to Resume Treatment

Subjects may resume treatment with study drug when the drug-related AE(s) resolve to Grade ≤ 1 or baseline value, with the following exceptions:

- Subjects may resume treatment in the presence of Grade 2 fatigue
- Subjects who have not experienced a Grade 3 drug-related skin AE may resume treatment in the presence of Grade 2 skin toxicity
- Subjects with baseline Grade 1 AST/ALT or total bilirubin who require dose delays for reasons other than a 2-grade shift in AST/ALT or total bilirubin may resume treatment in the presence of Grade 2 AST/ALT OR total bilirubin
- Subjects with combined Grade 2 AST/ALT AND total bilirubin values meeting discontinuation parameters should have treatment permanently discontinued
- Drug-related pulmonary toxicity, diarrhea, or colitis, must have resolved to baseline before treatment is resumed. *Subjects with persistent Grade 1 pneumonitis after completion of a steroid taper over at least 1 month may be eligible for retreatment if investigator allows, but should be discussed with the PI.*
- Drug-related endocrinopathies adequately controlled with only physiologic hormone replacement may resume treatment *if investigator allows, but should be stated in the protocol clearly.*

If the criteria to resume treatment are met, the subject should restart treatment at the next scheduled timepoint per protocol.

If treatment is delayed or interrupted for > 6 weeks, the subject must be permanently discontinued from study therapy, except as specified in discontinuation section.

7.7 Management Algorithms

Guidelines for the management of immune related events can be found in the current Investigator Brochure AND in the approved USPI in the US. Investigators should decide the appropriate source of AE management for each protocol.

Immuno-oncology (I-O) agents are associated with AEs that can differ in severity and duration than AEs caused by other therapeutic classes. Nivolumab is considered an

immuno-oncology agent in this protocol. Early recognition and management of AEs associated with immuno-oncology agents may mitigate severe toxicity. Management algorithms have been developed to assist investigators in assessing and managing the following groups of AEs:

Gastrointestinal, Renal, Pulmonary, Hepatic, Endocrinopathies, Skin, Neurological.

For subjects expected to require more than 4 weeks of corticosteroids or other immunosuppressants to manage an AE, consider recommendations provided in the algorithms. These algorithms are found in the Nivolumab IB [and in Appendix G] of this protocol. The guidance provided in these algorithms should not replace the Investigator's medical judgment but should complement it.

7.8 Discontinuation Criteria

Treatment should be permanently discontinued for the following:

- Grade 4 neutropenia lasting > 7 days
- Any Grade 2 drug-related uveitis or eye pain or blurred vision that does not respond to topical therapy and does not improve to Grade 1 severity within the re-treatment period OR requires systemic treatment
- Any Grade 3 non-skin, drug-related adverse event lasting > 7 days, with the following exceptions for drug-related laboratory abnormalities, uveitis, pneumonitis, bronchospasm, hypersensitivity reactions, and infusion reactions, and endocrinopathies:
 - Grade 3 drug-related uveitis, pneumonitis, bronchospasm, hypersensitivity reaction, or infusion reaction of any duration requires discontinuation
 - Grade 3 drug-related endocrinopathies adequately controlled with only physiologic hormone replacement do not require discontinuation
 - Grade 3 drug-related laboratory abnormalities do not require treatment discontinuation except those noted below
 - Grade 3 drug-related thrombocytopenia > 7 days or associated with bleeding requires discontinuation
 - Any drug-related liver function test (LFT) abnormality that meets the following criteria require discontinuation:
 - AST or ALT > 8 x ULN
 - Total bilirubin > 5 x ULN
 - Concurrent AST or ALT > 3 x ULN and total bilirubin > 2 x ULN

- AST or ALT $> 3 \times$ ULN with the appearance of fatigue, nausea, vomiting, right upper quadrant pain or tenderness, fever, rash, and/or eosinophilia ($>5\%$) should lead to treatment discontinuation.
- Any Grade 4 drug-related adverse event or laboratory abnormality, except for the following events which do not require discontinuation:
 - Isolated Grade 4 amylase or lipase abnormalities that are not associated with symptoms or clinical manifestations of pancreatitis and decrease to $<$ Grade 4 within 1 week of onset.
 - Isolated Grade 4 electrolyte imbalances/abnormalities that are not associated with clinical sequelae and are corrected with supplementation/appropriate management within 72 hours of their onset
 - Grade 4 lymphopenia or leucopenia
 - Grade 4 drug-related endocrinopathy adverse events, such as adrenal insufficiency, ACTH deficiency, hyper- or hypothyroidism, or glucose intolerance, which resolve or are adequately controlled with physiologic hormone replacement (corticosteroids, thyroid hormones) or glucose-controlling agents, respectively, may not require discontinuation after discussion with and approval from the Investigator [as allowed by protocol]
- Any dosing interruption lasting > 6 weeks with the following exceptions:
 - Dosing delays or interruptions to allow for prolonged steroid tapers to manage drug-related adverse events are allowed. Prior to re-initiating treatment in a subject with a dosing interruption lasting > 6 weeks, the Investigator must be consulted. Tumor assessments should continue as per protocol even if dosing is interrupted or delayed
 - Dosing interruptions or delays lasting > 6 weeks that occur for non-drug-related reasons may be allowed if approved by the Investigator. Prior to re-initiating treatment in a subject with a dosing interruption lasting > 6 weeks, the Investigator must be consulted. Tumor assessments should continue as per protocol even if dosing is interrupted
- Any adverse event, laboratory abnormality, or intercurrent illness which, in the judgment of the Investigator, presents a substantial clinical risk to the subject with continued nivolumab dosing

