Nivolumab can cause immune-mediated colitis. Monitor patients for signs and symptoms of colitis. Administer corticosteroids for Grade 2 (of more than 5 days duration), 3, or 4 colitis. Withhold monotherapy for Grade 2 or 3 and permanently discontinue for Grade 4 or recurrent colitis upon re-initiation of Nivolumab. In patients receiving mon Nivolumab therapy, immune-mediated colitis occurred in 2.9% (58/1994) of patients. In patients who received OPDIVO as a single agent, immune-mediated colitis occurred in 2.9% (58/1994)

of patients; the median time to onset was 5.3 months (range: 2 days to 20.9 months). Immune-mediated colitis led to permanent discontinuation of nivolumab 0.7% and withholding of OPDIVO in 1% of patients. Approximately 91% of patients with colitis received high-dose corticosteroids (at least 40 mg prednisone equivalents per day) for a median duration of 23 days (range: 1 day to 9.3 months). Four patients required addition of infliximab to high-dose corticosteroids. Complete resolution occurred in 74% of patients. Approximately 16% of patients had recurrence of colitis after re-initiation of nivolumab.

Immune-Mediated Hepatitis

Nivolumab can cause immune-mediated hepatitis. Monitor patients for abnormal liver tests prior to and periodically during treatment. Administer corticosteroids for Grade 2 or greater transaminase elevations. Withhold for Grade 2 and permanently discontinue for Grade 3 or 4 immune-mediated hepatitis.

In patients who received nivolumab as a single agent, immune-mediated hepatitis occurred in 1.8% (35/1994) of patients; the median time to onset was 3.3 months (range: 6 days to 9 months). Immune-mediated hepatitis led to permanent discontinuation of nivolumab in 0.7% and withholding of OPDIVO in 1% of patients. All patients with hepatitis received high-dose corticosteroids (at least 40 mg prednisone equivalents) for a median duration of 23 days (range: 1 day to 2 months). Two patients required the addition of mycophenolic acid to high-dose corticosteroids. Complete resolution occurred in 74% of patients. Approximately 29% of patients had recurrence of hepatitis after re-initiation of nivolumab.

Immune-Mediated Endocrinopathies

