APPENDIX D MANAGEMENT ALGORITHMS

Dose Modifications for Nivolumab/Opdivo (Package Insert Bristol-Myers Squibb)

Recommendations for OPDIVO modifications are provided in Table below. There are no recommended dose modifications for hypothyroidism or hyperthyroidism. Interrupt or slow the rate of infusion in patients with mild or moderate infusion reactions. Discontinue OPDIVO in patients with severe or life-threatening infusion reactions.

Recommended Dose Modifications for Nivolumab Adverse Reaction	Severity*	Dose Modification
Grade 4 diarrhea or colitis	Permanently discontinue	
Pneumonitis	Grade 2 pneumonitis Grade 3 or 4 pneumonitis	Withhold dose (a) Permanently discontinue
Hepatitis	Aspartate aminotransferase (AST)/or alanine aminotransferase (ALT) more than 3 and up to 5 times the upper limit of normal or total bilirubin more than 1.5 and up to 3 times the upper limit of normal AST or ALT more than 5 times the upper limit of normal or total bilirubin more than 3 times the upper limit of normal	Withhold dose (a) Permanently discontinue
Hypophysitis	Grade 2 or 3 hypophysitis Grade 4 hypophysitis	Withhold dose (a) Permanently discontinue
Adrenal Insufficiency	Grade 2 adrenal insufficiency Grade 3 or 4 adrenal insufficiency	Withhold dose (a) Permanently discontinue
Type 1 Diabetes Mellitus	Grade 3 hyperglycemia Grade 4 hyperglycemia	Withhold dose (a) Permanently discontinue
Nephritis and Renal Dysfunction	Serum creatinine more than 1.5 and up to 6 times the upper limit of normal Serum creatinine more than 6 times the upper limit of normal	Withhold dose (a) Permanently discontinue
Skin	Grade 3 rash or suspected Stevens-Johnson syndrome (SJS) or toxic epidermal necrolysis (TEN) Grade 4 rash or confirmed SJS or TEN	Withhold dose (a) Permanently discontinue
Encephalitis	New-onset moderate or severe neurologic signs or symptoms Immune-mediated encephalitis	Withhold dose (a) Permanently discontinue
Other	Other Grade 3 adverse reaction First occurrence Recurrence of same Grade 3 adverse reactions Life-threatening or Grade 4 adverse reaction Requirement for 10 mg per day or greater prednisone or equivalent for more than 12 weeks Persistent Grade 2 or 3 adverse reactions lasting 12 weeks or longer	Withhold dose (a) Permanently discontinue Permanently discontinue Permanently discontinue Permanently discontinue Permanently discontinue

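### Section 7.8 and Appendices C and D give opposed permanent-stop rules for nivolumab, and no sentence says which governs

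*Combined protocol and SAP*

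**What the plan says.** Section 7.8 lists when nivolumab must be stopped for good. It exempts Grade 3 laboratory abnormalities in general, then names the liver results that do require a stop: "AST or ALT > 8 x ULN", total bilirubin above 5 x ULN, "Concurrent AST or ALT > 3 x ULN and total bilirubin > 2 x ULN", and AST or ALT above 3 x ULN "with the appearance of fatigue, nausea, vomiting, right upper quadrant pain or tenderness, fever, rash" and/or eosinophilia. Section 7.6 repeats the combined trigger: "Subjects with combined Grade 2 AST/ALT AND total bilirubin values meeting discontinuation parameters should have treatment permanently discontinued".

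Appendix D, taken from the package insert, sets a different liver rule. It stops permanently at "AST or ALT more than 5 times the upper limit of normal or total bilirubin more than 3 times the upper limit of normal", and it only withholds when transaminases are "more than 3 and up to 5 times the upper limit of normal or total bilirubin more than 1.5 and up to 3 times", measured against ULN. Its footnote allows resumption at Grade 0 or 1. Appendix C says the same by grade: "Withhold for Grade 2 and permanently discontinue for Grade 3 or 4 immune-mediated hepatitis".

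On endocrine events, 7.8 does not require a stop at Grade 3 if the event is controlled on hormone replacement. At Grade 4 it may allow continuation once the Investigator approves. Both appendices stop permanently for Grade 3 or 4 adrenal insufficiency, Grade 4 hypophysitis and Grade 4 hyperglycemia.

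On colitis, 7.8's general rule stops any Grade 3 non-skin drug-related event lasting more than 7 days. Appendix C withholds for Grade 3.

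On long delays, Section 1.6 requires withdrawal after a nivolumab delay of more than 6 weeks, without exception. Section 7.8 excepts prolonged steroid tapers and approved non-drug-related delays.

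**The concern.** Section 1.5 plans a coordinating center with about 2-3 further sites. Two sites could see the same patient picture, each follow a passage of this protocol, and decide differently whether nivolumab may ever be given again. The drug's immune toxicities can be fatal (Appendix C), and here it is combined with pelvic radiation. The coordinating center would also have no settled basis for calling a protocol deviation. The monthly meetings and single monitoring committee in Section 12.0 offer a forum for discussing cases, but they set no threshold.

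**Working it through.** The plan gives no figure to reproduce, so the check has three parts.

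**1. The rules side by side** (thresholds in multiples of ULN)

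Liver stop under 7.8: AST/ALT > 8; or bilirubin > 5; or AST/ALT > 3 with bilirubin > 2; or AST/ALT > 3 with a listed symptom or sign.

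Liver stop under Appendix D: AST/ALT > 5, or bilirubin > 3.

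| Situation | Section 7.8 | Appendices |
|---|---|---|
| AST/ALT > 5 to 8, bilirubin <= 2, no listed symptom | None of the four triggers is met: no required stop | AST/ALT > 5: stop (D) |
| Bilirubin > 3 to 5, AST/ALT <= 3 | None of the four triggers is met: no required stop | Bilirubin > 3: stop (D) |
| AST/ALT > 3 to 5, bilirubin > 2 to 3 | Combined trigger: stop (repeated in 7.6) | Neither stop limit crossed: withhold (D) |
| AST/ALT > 3 to 5 with a listed symptom, bilirubin <= 3 | Symptom trigger: stop | Neither stop limit crossed: withhold (D) |
| Controlled Grade 3 adrenal insufficiency | No required stop | Stop (C, D) |
| Controlled Grade 4 adrenal insufficiency, hypophysitis or hyperglycemia | May continue with Investigator approval | Stop (C, D) |
| Grade 3 colitis lasting > 7 days | Stop | Withhold (C) |

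The colitis row uses Appendix C only, because that part of the Appendix D table is incomplete in the text available. The sources agree on Grade 3-4 pneumonitis and on severe infusion reactions.

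Within the protocol body, 1.6 and 7.8 conflict on delays beyond 6 weeks. Section 7.6 sides with 7.8, because it excepts whatever the discontinuation section allows.

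**2. Search for a ranking**

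- 7.7 leaves the source of adverse-event management to investigators.
- Appendix C describes itself as guidance, yet directs readers to the approved label for discontinuation where that applies. Appendix D is the label's table.
- 7.6 defers to 7.8, but only on long delays.
- 7.5 sends the reader to Appendix D for the algorithms. 7.7 cites Appendix G, which Section 6 uses for the correlative studies.

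These pointers do not agree, and none states whether 7.8 or the appendices prevail.

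**3. How often it could arise**

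Appendix C reports for monotherapy: "Immune-mediated hepatitis led to permanent discontinuation of nivolumab in 0.7% and withholding of OPDIVO in 1% of patients". It gives the same two percentages for colitis. Expected cases = N x rate; chance of at least one = 1 - (1 - rate)^N. N runs from 30 evaluable to 34 enrolled (Section 8.3).

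- Permanent stop, 0.7%: 30 x 0.007 = 0.21 and 34 x 0.007 = 0.24 cases; 1 - 0.993^30 = 19% and 1 - 0.993^34 = 21%.
- Withheld, 1%: 30 x 0.01 = 0.30 and 34 x 0.01 = 0.34 cases; 1 - 0.99^30 = 26% and 1 - 0.99^34 = 29%.

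These figures apply to hepatitis and to colitis separately. Any-grade cases in 34 patients, as a loose upper guide:

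- hepatitis 34 x 35/1994 = 0.60
- colitis 34 x 58/1994 = 0.99
- adrenal insufficiency 34 x 20/1994 = 0.34
- hypophysitis 34 x 12/1994 = 0.20
- diabetes 34 x 17/1994 = 0.29

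**The case against.** The strongest reply is that the hierarchy can be inferred. Section 7.8 is a body section in mandatory terms, Appendix C calls itself guidance, Appendix D offers recommendations, and 7.7 says the algorithms complement medical judgment. This has weight, but it is an inference. Appendix C's pointer to the label and 7.7's grant of choice to investigators pull the other way.

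Four narrower points stand and limit the finding.

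- **Stopping is always open.** In the isolated-liver and endocrine rows, 7.8 does not forbid a stop, and its last bullet lets the Investigator stop on judgment. A reader might infer that no action can satisfy both texts. In those rows that is wrong. In the combined-liver, symptomatic-liver and Grade 3 colitis rows, however, a site that resumes under the appendix departs from 7.8.
- **The drug is not simply continued through liver toxicity.** Section 7.5 delays dosing for drug-related liver-test toxicity from Grade 2 (from Grade 3 if baseline was Grade 1), and 7.6 generally requires recovery before restart. The dispute is mostly about re-exposure. Restart with a controlled endocrinopathy under 7.6 is also at the investigator's discretion.
- **The isolated-liver rows depend on how the event is recorded.** Grade 3 hepatitis recorded as a clinical event lasting more than 7 days would arguably stop under 7.8's general rule too. Isolated bilirubin elevation is the weakest fit to a row headed hepatitis.
- **Two appendix rules are gaps in 7.8.** Appendix C stops for colitis recurring on re-initiation. Appendix D stops when prednisone of 10 mg/day or more is needed for over 12 weeks. A reader might count these as further contradictions. Section 7.8 simply does not carry them: its taper exception lifts only the 6-week limit and says nothing about steroid need beyond 12 weeks.

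**Conclusion.** Wrong as written: an internally contradictory safety rule that should be corrected. The opposition between 7.8 and Appendices C and D holds for the rows tabulated, as does the separate conflict between 1.6 and 7.8 on delays over 6 weeks. The two appendix-only stops are omissions to close.

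The practical size is small. The case counts assume that the monotherapy rates apply and that patients are independent. The stop and withhold rates also reflect the rules used in other trials. They do not count discordant cases, and the documents give no rates for nivolumab with concurrent pelvic radiation.

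A reader might infer that the trial's results are compromised. The documents do not support that. The sample size and critical value do not depend on the stop rule, PFS in 4.9 is not defined by treatment discontinuation, and 8.4.2 counts toxicity in everyone who starts nivolumab. Nor do the documents show which threshold is medically right; this point takes no position on that.

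**What to change.** 1. Amend 7.8 into a single stop table, reconciled row by row by the medical team. Cover the rows above and the two appendix-only stops (recurrent colitis, and prednisone of 10 mg/day or more for over 12 weeks).
2. Align Section 1.6 with the table on delays over 6 weeks, and correct the Appendix G reference in 7.7.
3. State in 7.7 and 7.8 that this table governs permanent discontinuation at all sites, and that Appendices C and D are background where they differ. Add this only with the reconciled table: ranking the present 7.8 first would adopt the looser rule for isolated liver tests and controlled endocrine events.
4. Until the amendment issues, instruct sites to apply the stricter of the conflicting rules. Where the appendix is stricter, 7.8's judgment bullet already permits the stop. Where 7.8 or 1.6 is stricter, that section already requires it.

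The cost is amendment wording, ethics review under Section 9.3 and site notification, with no extra visits, tests or patients. The interim rule may end nivolumab early for an occasional patient who could otherwise have resumed.

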7.9 Treatment of Nivolumab Related Infusion Reactions

Since nivolumab contains only human immunoglobulin protein sequences, it is unlikely to be immunogenic and induce infusion or hypersensitivity reactions. However, if such a reaction were to occur, it might manifest with fever, chills, rigors, headache, rash, pruritis,

arthralgias, hypo- or hypertension, bronchospasm, or other symptoms of allergic-like reactions.

All Grade 3 or 4 infusion reactions should be reported as an SAE if criteria are met. Infusion reactions should be graded according to NCI CTCAE 4.0 guidelines.

Treatment recommendations are provided below and may be modified based on local treatment standards and guidelines as appropriate:

For Grade 1 symptoms: (Mild reaction; infusion interruption not indicated; intervention not indicated)

Remain at bedside and monitor subject until recovery from symptoms. The following prophylactic premedications are recommended for future infusions: diphenhydramine 50 mg (or equivalent) and/or paracetamol 325 to 1000 mg (acetaminophen) at least 30 minutes before additional nivolumab administrations.

For Grade 2 symptoms: (Moderate reaction requires therapy or infusion interruption but responds promptly to symptomatic treatment [eg, antihistamines, non-steroidal anti-inflammatory drugs, narcotics, corticosteroids, bronchodilators, IV fluids]; prophylactic medications indicated for 24 hours).

Stop the nivolumab infusion, begin an IV infusion of normal saline, and treat the subject with diphenhydramine 50 mg IV (or equivalent) and/or paracetamol 325 to 1000 mg (acetaminophen); remain at bedside and monitor subject until resolution of symptoms. Corticosteroid or bronchodilator therapy may also be administered as appropriate. If the infusion is interrupted, then restart the infusion at 50% of the original infusion rate when symptoms resolve; if no further complications ensue after 30 minutes, the rate may be increased to 100% of the original infusion rate. Monitor subject closely. If symptoms recur then no further nivolumab will be administered at that visit. Administer diphenhydramine 50 mg IV, and remain at bedside and monitor the subject until resolution of symptoms. The amount of study drug infused must be recorded on the electronic case report form (eCRF). The following prophylactic premedications are recommended for future infusions: diphenhydramine 50 mg (or equivalent) and/or paracetamol 325 to 1000 mg (acetaminophen) should be administered at least 30 minutes before additional nivolumab administrations. If necessary, corticosteroids (recommended dose: up to 25 mg of IV hydrocortisone or equivalent) may be used.

For Grade 3 or Grade 4 symptoms: (Severe reaction, Grade 3: prolonged [ie, not rapidly responsive to symptomatic medication and/or brief interruption of infusion]; recurrence of symptoms following initial improvement; hospitalization indicated for other clinical sequelae [eg, renal impairment, pulmonary infiltrates]). Grade 4: (life threatening; pressor or ventilatory support indicated).

Immediately discontinue infusion of nivolumab. Begin an IV infusion of normal saline, and treat the subject as follows. Recommend bronchodilators, epinephrine 0.2 to 1 mg of a 1:1,000 solution for subcutaneous administration or 0.1 to 0.25 mg of a 1:10,000 solution

injected slowly for IV administration, and/or diphenhydramine 50 mg IV with methylprednisolone 100 mg IV (or equivalent), as needed. Subject should be monitored until the investigator is comfortable that the symptoms will not recur. Nivolumab will be permanently discontinued. Investigators should follow their institutional guidelines for the treatment of anaphylaxis. Remain at bedside and monitor subject until recovery from symptoms.

In the case of late-occurring hypersensitivity symptoms (eg, appearance of a localized or generalized pruritis within 1 week after treatment), symptomatic treatment may be given (eg, oral antihistamine, or corticosteroids).

